9.2.2. Schirmer Test

The Schirmer test is performed only at baseline. All data will be listed.

9.2.3. Protocol Deviations

The number and percentage of patients with a major deviation by type of deviation category will be summarised for the mITT population. Protocol deviations due to COVID-19 will also be presented.

In addition, all major and minor protocol deviations will be provided in a by-patient listing. Also, a by-patient listing will be provided detailing missing visits and assessments due to COVID-19, if applicable.

9.3. Neurotrophic Keratitis Medical History in the Study Eye

Descriptive statistics of NK medical history characteristics in the study eye, including NK stage at screening, time since first diagnosis (weeks), number of episodes/recurrences since first diagnosis, prior treatment or surgical procedures and the underlying cause of NK will be presented by treatment group and overall. All data will be summarised using both continuous and categorical descriptive statistics based on the mITT population.

Time since first diagnosis will be calculated in weeks as:

Time since first diagnosis = (date of informed consent – date of first diagnosis) / 7

Imputation in case of partial dates for the calculation of the time since first diagnosis will be applied according to Section 8.3.

All NK data for the study eye will be presented in a by-patient listing.

9.4. Other Medical History

Medical history other than NK in the study eye will be coded using MedDRA 22.1. System Organ Class (SOC) and Preferred Term (PT) will be presented alphabetically in a table by treatment group and overall based on the mITT population.

The by-patient listing will display the SOC and PT, sorted by start date as well as SOC and PT alphabetically.

9.5. Medications and Other Interventions

9.5.1. Prior Medication

Prior medication will be coded using the WHO Drug Dictionary, and patient incidence will be summarised and tabulated by Anatomic Therapeutic Class (ATC) Level 2 and Level 3 term and preferred term by treatment group and overall based on the mITT population. Patients will be counted only once for each ATC term or preferred term in the event that they have multiple records of the same ATC term or preferred term in the database. If a prior medication is used to treat an AE, the AE number will be presented in the prior and concomitant medication listing. If the prior medication is related to the medical history, the medical history number will be listed as well. The same applies if the use of prior medication is related to any ocular intervention or surgery or procedure, then the respective event number will be displayed in the listing for reference.

Prior medications will be defined as any medication taken before the date of first treatment administration.

9.5.2. Concomitant Medication

Concomitant medication will be coded using the WHO Drug Dictionary, and patient incidence will be summarised and tabulated by ATC Level 2 and 3 term and preferred term by treatment group and overall based on the mITT population. Patients will be counted only once for each ATC term or preferred term in the event that they have multiple records of the same ATC term or preferred term in the database. If a concomitant medication is used to treat an AE, the AE number will be presented in the prior and concomitant medication listing. If the concomitant medication is related to the medical history, the medical history number will be listed as well. The same applies if the use of concomitant medication is related to any ocular intervention or surgery or procedure then the respective event number will be displayed in the listing for reference.

A concomitant medication is defined as taken between the date of first dose of treatment and the date of last dose of treatment.

Any medication missing both start and stop dates or having a start date prior to the first treatment administration and missing the stop date or having a stop date on or after the last treatment administration and missing start date will be counted as concomitant. If only partial dates are available the approaches described in Section 8.3 are used to determine if a medication is concomitant.

9.5.3. Prior and Concomitant Ocular Interventions

All prior and concomitant ocular interventions will be listed. If the intervention is related to a record of medical history or an AE, then the AE/medical history number will be presented in the listing as well.

Ocular interventions will be summarised using both continuous and categorical descriptive statistics based on the mITT population.

Prior interventions will be defined as any intervention before the date of first treatment administration. A concomitant intervention is defined as conducted between the date of first dose of treatment and the date of last dose of treatment.

Any intervention missing the start date it will be counted as concomitant. If only partial dates are available the approaches described in Section 8.3 are used to determine if an intervention is concomitant.

9.5.4. Prior and Concomitant Surgeries and Procedures (Other Than Ocular)

All prior and concomitant surgeries and procedures will be listed. If they are related to a record of medical history or an AE, then the AE/medical history number will be presented in the listing as well.

Any surgery or procedure will be summarised using both continuous and categorical descriptive statistics based on the mITT population.

Prior surgeries or procedures will be defined as any surgery or procedure before the date of first treatment administration. A concomitant surgery or procedure is defined as conducted between the date of first dose of treatment and the date of last dose of treatment.

Any surgery or procedure missing the start date will be counted as concomitant. If only partial dates are available the approaches described in Section 8.3 are used to determine if a surgery or procedure is concomitant.

9.6. Extent of Exposure

Exposure will be calculated in days as:

Exposure = date of last treatment administration - date of first treatment administration + 1.

In case the treatment dosing is interrupted by either the patient or investigator, the number of subjects with interruptions will be summarised, and the duration of interruption (days) is calculated and summarised. This interruption duration is also subtracted from the extent of exposure duration.

• Interruption = interruption end date - interruption start date + 1.

Study duration (days) will be obtained as follows:

• Study duration = end of study date - date of informed consent + 1.

All data for study drug dispensation, dosing, and supply accountability will be listed. A summary will be provided for the extent of exposure by treatment group and overall based on the SAF population.

9.7. Treatment Compliance

Patients will be instructed to bring their unused/partially used/empty containers back for inspection at each study visit, and the number of opened BFS containers will be recorded. Patients will also be instructed to fill out a paper diary recording the date and time of study drug administration, which should be brought to the site at each study visit and reviewed with the patient. Patient compliance with the treatment will be assessed overall.

Overall compliance will be assessed by number of opened BFS containers. Noncompliance is defined as taking less than 80% or more than 120% of study drug during any outpatient evaluation period. Discontinuation of treatment for noncompliance is at the investigator's discretion and is to be noted on the eCRF.

Overall compliance (%) = (Number of used BFS containers) / [4 * (number of BFS to be used based on actual number of days of treatment)] * 100

With actual number of days of treatment calculated as:

Actual number of days = (last treatment administration date) - (first treatment administration date) + 1

Overall compliance will be summarised in a table by treatment group and overall based on the SAF population, and all data will be presented in a by-patient listing.

10. Efficacy

The analysis of all efficacy endpoints will be performed for the mITT population. Tertiary sensitivity analyses of the primary efficacy endpoint will also be performed on the PP population. The vehicle group will be used as reference group for all statistical tests.

All categorical endpoints will be analysed using the Cochran-Mantel-Haenszel (CMH) test stratified by region at randomisation as well as NK stage at randomisation. SAS procedure proc freq will be used.

All time-to-event endpoints will be evaluated by means of Kaplan-Meier (Kaplan & Meier 1958) survival analysis using a log-rank test. The Cox's proportional hazard model is used to estimate the hazard ratios, 95% confidence limits and p-values and includes covariates such as treatment group and randomisation strata, i.e. NK stage and region. SAS procedure proc lifetest will be used for the Kaplan-Meier analysis and proc phreg will be used for the Cox model.

All data from the enrolled patient population will be listed. Screen failures or patients who are not treated will be presented at the end of the listings. All SAS procedures and algorithms will be detailed in the supplemental ADaM results metadata as well as the ADaM specifications and complex algorithem document.

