9 TREATMENTS

9.1 Details of Study Treatments

The drug product REC 0/0559 is an ophthalmic solution packaged in single-use blow fill seal (BFS) containers. The solution will be stored at room temperature (below 25°C).

Patients are to use a single BFS container per study drug administration (ie, 4 BFS containers per day).

Three strengths (5, 25, and 50 μ g/mL) of ophthalmic solution with MT8 will be prepared, one for each active treatment arm.

For the comparator, an ophthalmic solution of the same composition as the study drug without the active substance MT8 (vehicle) will be used. The vehicle is identical in appearance and packaging to the study drug, and study drugs are labelled in a masked manner.

All study drug will be provided by the Sponsor and will be packaged and labelled in accordance with the principles and the detailed guidelines of Good Manufacturing Practice (GMP) for Medicinal Products. The primary label as well as the secondary container labelling will be in country specific language. Label contents will be compliant with local regulatory requirements. All study drug provided will be stored in a secure locked area with access limited to those authorised by the investigator and under controlled storage conditions described in the product's labelling.

For each patient entering in the study, the investigator will be provided with a set of numbered study drug kits each containing 4 pouches of 10 eye drop solution single dose units (BFS containers) with 0.5 mL each of REC 0/0559 (5, 25, or $50 \mu g/mL$) or vehicle. Each study drug kit will provide treatment for a period of 7 days, and contain treatment for 3 additional days as spare.

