12.9 Other Reportable Information

Certain information, although not considered an SAE, must be recorded, reported, and followed up as indicated for an SAE. This includes the following:

- Overdose of an investigational product with or without an AE. For this study, an overdose is defined as an increase of the intake frequency of the study medication to more than 8 times per day (ie, > 2 × the daily dose specified in the protocol).
- Inadvertent or accidental exposure to an investigational product with or without an AE.
- Medication errors with or without an AE (medication error is an administration of study drug that does not match what was allocated by randomisation, administration of an expired study drug, or administration of a study drug that has not met storage conditions as described in the protocol, and use outside what is foreseen in the protocol, including other storage conditions).
- Misuse, where the medicinal product is intentionally used not in accordance with the protocol.
- Any suspicion of transmission of an infectious agent via an investigational product.

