See section 15 for Format of output in the SAP. Percentages are based on N. Patients will be counted only once for each ATC or preferred term in the event that they have multiple records of the same ATC or preferred term in the data. Sort by highest frequency by ATC 2 and 3 Level and PT. Present table by 'Overall' (prior and concomitant), 'Prior' and 'Concomitant' medication in subtitle. Add WHOdd version instead of <version> place holder in the footnote.

Sponsor: Recordati Rare Diseases; Protocol No.: REC0559-B-001

Table 14.1.4.2 Summary of Prior and Concomitant Surgery and Procedures (Other than Ocular) (mITT)

	REC 0/0559 0.5 μg/day (N=xx)	REC 0/0559 2.5 μg/day (N=xx)	REC 0/0559 5.0 μg/day (N=xx)	Vehicle (N=xx)	Total (N=xx)
	n (%)	n (%)	n (%)	n (%)	n (%)
Any Surgery or Procedure	n (xx)	n (xx)	n (xx)	n (xx)	n (xx)
Prior	n (xx)	n (xx)	n (xx)	n (xx)	n (xx)
Concomitant	n (xx)	n (xx)	n (xx)	n (xx)	n (xx)
Reason for Surgery or Procedure					
Adverse Event	n (xx)	n (xx)	n (xx)	n (xx)	n (xx)
Medical History	n (xx)	n (xx)	n (xx)	n (xx)	n (xx)

n: Number of patients with data available, N: Number of patients within treatment group

Note: Percentage is based on number of patients within treatment group.

Note: A patient is only counted once per surgery or procedure.

Analysis dataset: ADxx.SAS7BDAT; Data Source: Listing 16.2.x

Programming Note:

See section 15 for Format of output in the SAP. Percentages are based on N.

This document is confidential.

SAP Version: 1.0, 31-May-2024

Controlled Document ID: 3903A.02, Effective Date 31-Aug-2020

Sponsor: Recordati Rare Diseases; Protocol No.: REC0559-B-001

Table 14.1.5.1 Summary of Treatment Compliance (SAF)

	REC 0/0559 0.5 µg/day (N=xx)	REC 0/0559 2.5 µg/day (N=xx)	REC 0/0559 5.0 μg/day (N=xx)	Vehicle (N=xx)	Total (N=xx)
Overall Compliance, n					
(%)					
< 80%	n (xx)	n (xx)	n (xx)	n (xx)	n (xx)
80% - 120%	n (xx)	n (xx)	n (xx)	n (xx)	n (xx)
> 120%	n (xx)	n (xx)	n (xx)	n (xx)	n (xx)
Overall compliance (%)					
n	X	X	Х	Х	X
Mean (SD)	xx.x (x.xx)	xx.x (x.xx)	xx.x (x.xx)	xx.x (x.xx)	xx.x (x.xx)
Minimum	XX	xx	XX	XX	xx
Median	XX.X	XX.X	xx.x	XX.X	xx.x
Maximum	XX	XX	XX	XX	XX

n: Number of patients with data available, N: Number of patients within treatment group, SD: Standard Deviation, BFS: Blow Fill Seal Note: Percentage is based on number of patients within treatment group.

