Note: Overall compliance (%) is calculated based on (the number of used BFS containers) / [4 * (number of BFS containers to be used based on actual days of treatment)] * 100.

Analysis dataset: ADxx.SAS7BDAT; Data Source: Listing 16.2.x

Programming Note:

See section 15 for Format of output in the SAP. Display metrics for each scheduled Visit to Visit interval as well as the overall compliance over all visits at last.

This document is confidential.

SAP Version: 1.0, 31-May-2024

Controlled Document ID: 3903A.02, Effective Date 31-Aug-2020

Table 14.2.1.1 Percentage of Patients Achieving Complete Corneal Healing of PED or Corneal Ulcer at Week 8 controlling for Disease Stage and Region - Central Reading - Primary Estimand (mITT)

	REC 0/0559	REC 0/0559	REC 0/0559	
	0.5 µg/day	2.5 µg/day	5.0 μg/day	Vehicle
	(N=xx)	(N=xx)	(N=xx)	(N=xx)
Intercurrent events (ICE) up to Week 8, n (%)				
ICE1: Treatment discontinuation due to treatment-related AE	n (xx)	n (xx)	n (xx)	n (xx)
ICE2: Treatment discontinuation due to other reasons	n (xx)	n (xx)	n (xx)	n (xx)
ICE3: Start of rescue treatments/procedures	n (xx)	n (xx)	n (xx)	n (xx)
ICE4: Treatment discontinuation due to death	n (xx)	n (xx)	n (xx)	n (xx)
isease Stage, Region at Randomisation				
2 (Moderate), EU				
Healed (%)	XX.X	XX.X	xx.x	XX.X
Not healed (%)	XX.X	XX.X	xx.x	XX.X
Risk difference for complete corneal healing	X.XX	X.XX	x.xx	
95% Confidence Interval	(x.xx, x.xx)	(x.xx, x.xx)	(x.xx, x.xx)	
3 (Severe), EU				
Healed (%)	XX.X	XX.X	xx.x	XX.X
Not healed (%)	XX.X	XX.X	xx.x	XX.X
Risk difference for complete corneal healing	X.XX	X.XX	x.xx	
95% Confidence Interval	(x.xx, x.xx)	(x.xx, x.xx)	(x.xx, x.xx)	
2 (Moderate), NA				
Healed (%)	XX.X	XX.X	xx.x	XX.X
Not healed (%)	XX.X	XX.X	xx.x	XX.X
Risk difference for complete corneal healing	X.XX	x.xx	x.xx	
95% Confidence Interval	(x.xx, x.xx)	(x.xx, x.xx)	(x.xx, x.xx)	
3 (Severe), NA				
Healed (%)	XX.X	xx.x	xx.x	XX.X
Not healed (%)	XX.X	XX.X	xx.x	XX.X
Risk difference for complete corneal healing	X.XX	X.XX	x.xx	
95% Confidence Interval	(x.xx, x.xx)	(x.xx, x.xx)	(x.xx, x.xx)	
ommon Odds (OR) controlling for disease stage and region for				
omplete corneal healing				
Healed (%)	XX.X	XX.X	XX.X	XX.X
Not healed (%)	XX.X	XX.X	xx.x	XX.X
Estimate	X.XX	X.XX	X.XX	
95% Confidence Interval	(x.xx, x.xx)	(x.xx, x.xx)	(x.xx, x.xx)	
ommon Risk Difference				
Estimate	X.XX	X.XX	x.xx	
95% Confidence Interval	(x.xx, x.xx)	(x.xx, x.xx)	(x.xx, x.xx)	
ochran-Mantel-Haenszel (CMH) Test				

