Note: Duration of Interruption (days) = (interruption end date - interruption start date) + 1.

Analysis dataset: ADxx.SAS7BDAT;

Programming Note:

See section 15 for Format of output in the SAP. Sort listing by treatment group (lowest REC 0/0559 to highest and then Vehicle) and patient ID and visit.

Sponsor: Recordati Rare Diseases; Protocol No.: REC0559-B-001

Listing 16.2.5.1.2 Study Drug Dispensation and Compliance (Enrolled Set)

Patient ID/ Treatment group/ Region/ Disease stage \$/ Study eye	Visit	Date of Dispensation	Kit Numbers/ Reason Not Done	Date of Previous Visit	Numbers of used BFS	Comment	Expected number of used BFS/ Overall Compliance (%)
Xxxxx/ REC 0/0559 0.5 µg/day/ NA/ 2/ Right	Visit x	Ddmmmyyyy	Ххх, ууу	N/A	Xxx	Xxxxxx	
-	Visit y	Ddmmmyyyy	Xxxxxxxxxxxx	Ddmmmyyyy	Xxx	_	
		Ddmmmyyyy	Xxx	Ddmmmyyyy	Xxx	-	XX.X
Xxxxx/ yyyy/ zz/ v/ uuuuuu	Visit x	Ddmmmyyyy	Xxx	N/A	Xxx	-	
	Visit y	Ddmmmyyyy	Xxx	Ddmmmyyyy	Xxx	-	
		Ddmmmyyyy	Xxx	Ddmmmyyyy	Xxx	-	XX.X

BFS: Blow Fill Seals

\$: Stage 2 = Moderate, Stage 3 = Severe

Note: - = unknown or not evaluated, N/A = not applicable, NA = North America, EU = Europe

Note: Overall compliance (%) is calculated as (Number of used BFS containers) / [4 * (number of BFS to be used based on actual number of days of treatment)] * 100. Non-compliance is defined as <math>< 80% or > 120% overall compliance.

Analysis dataset: ADxx.SAS7BDAT;

Date/time of run: ddmmmyyyy:hh:mm

program name>

Programming Note:

See section 15 for Format of output in the SAP. Sort listing by treatment group (lowest REC 0/0559 to highest and then Vehicle) and patient ID and visit.

Sponsor: Recordati Rare Diseases; Protocol No.: REC0559-B-001

Listing 16.2.5.1.3 Patient Supply Accountability (Enrolled Set)

Patient ID/ Treatment group/ Region/ Disease stage \$/ Study eye	Visit	Kit ID/ Lot ID/ Date of Expiry	Kit Type (unit)	Quantity Dispensed (Kits)/ IP Units Dispensed (BFS)	Item Status/ Date Returned	Condition/ Quantity of returned Kit	IP Units unused (BFS)	Comment
Xxxxx/ REC 0/0559 0.5 µg/day/ NA/ 2/ Right	Visit x	Xxxx/ yyyyy/ ddmmmyyyy	Хххх (уууу)	Хх/ ууу	Returned/ ddmmmyyyy	Good/ xxx	Xxx	-
		Xxxx/ yyyyy/ ddmmmyyyy	Хххх (уууу)	Хх/ ууу	Returned/ ddmmmyyyy	Good/ xxx	Xxx	-
		Xxxx/ yyyyy/ ddmmmyyyy	Хххх (уууу)	Хх/ ууу	Returned/ ddmmmyyyy	Damaged/ xxx	Xxx	-
		Xxxx/ yyyyy/ ddmmmyyyy	Хххх (уууу)	Хх/ ууу	Returned/ ddmmmyyyy	Unopened/ xxx	Xxx	-
			Хххх (уууу)	Xx/ yyy	Returned/ ddmmmyyyy	Good/ xxx	Xxx	-

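### The overall-compliance formula counts the 4 containers per day twice, so full use scores 25% and every plausible patient is reported as below 80%

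*SAP*

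**What the plan says.** SAP Section 9.7 assesses overall compliance from opened single-dose (BFS) containers. It gives the percentage as "Number of used BFS containers) / [4 * (number of BFS to be used based on actual number of days of treatment", multiplied by 100. The line after the formula defines the actual number of days as last administration date minus first administration date plus 1. The same section sets the non-compliance limits at below 80% and above 120%.

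The formula appears twice more in the shells:

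- The footnote of Table 14.1.5.1, "Summary of Treatment Compliance (SAF"), divides by "4 * (number of BFS containers to be used based on actual days of treatment)] * 100". The table sorts patients into below 80%, 80% to 120%, and above 120%, and also gives the mean, median and range. Its programming note adds: "Display metrics for each scheduled Visit to Visit interval as well as the overall compliance over all visits at last".
- The footnote of Listing 16.2.5.1.2 divides by "4 * (number of BFS to be used based on actual number of days of treatment)] * 100". It then defines non-compliance on this same figure, as below "80% or > 120% overall compliance".

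The expected rate of use is in Protocol Section 9.1: "Patients are to use a single BFS container per study drug administration (ie, 4 BFS containers per day").

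**The concern.** The number of containers due over a patient's treatment days is 4 per day times the number of days. Multiplying that count by 4 again makes the denominator 16 per day, four times too large. Section 9.7 defines the number of days immediately after the formula, which suggests that the 4 was meant to multiply days. None of the three statements of the formula says so.

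The limits of 80% and 120% make sense only if full dosing scores 100%. With the written formula they no longer separate adherent patients from under-users or over-users. The categorical part of the table would put everyone in one row, and the listing would mark fully adherent patients as non-compliant. If the same formula is applied to the visit-to-visit intervals that the programming note requests, the error repeats in each one.

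**Working it through.** **Inputs**

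- Containers due per day: 4 (Protocol Section 9.1).
- Treatment days, D: 56 for the planned 8 weeks (Protocol synopsis). D cancels, so the percentages below hold for any duration.
- Reporting limits: 80% and 120% (SAP Section 9.7, Table 14.1.5.1, Listing 16.2.5.1.2).
- Overdose definition: "an increase of the intake frequency of the study medication to more than 8 times per day" (Protocol Section 12.9). The boundary is therefore 8 a day, and 8 itself is not yet an overdose.
- Kit size: 4 pouches of 10, so 40 containers per 7-day kit (Protocol Section 9.1). The total dispensed per patient is not stated. I assume one kit per 7 days, which is 8 kits.

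**Formula as written**

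Expected containers = 4 × D = 4 × 56 = 224.

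Denominator = 4 × 224 = 896, or 16 × D.

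Compliance = 100 × used / 896.

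| True use over 56 days | Containers | Score as written | Row in the table | Score with the 4 counted once |
|---|---|---|---|---|
| 80% of schedule | 179.2 | 20.0% | below 80% | 80% |
| Full schedule | 224 | 25.0% | below 80% | 100% |
| 120% of schedule | 268.8 | 30.0% | below 80% | 120% |
| Whole assumed supply (8 × 40) | 320 | 35.7% | below 80% | 142.9% |
| 8 a day | 448 | 50.0% | below 80% | 200% |
| Twice the assumed supply | 640 | 71.4% | below 80% | 285.7% |

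**Use needed to leave the bottom row**

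- To reach 80%: 0.80 × 896 = 716.8 containers, and 716.8 / 56 = 12.8 a day.
- To exceed 120%: more than 1.20 × 896 = 1,075.2 containers, and 1,075.2 / 56 = 19.2 a day.

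**Formula with the 4 counted once**

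Compliance = 100 × used / (4 × D). The limits then fall at 0.80 × 4 = 3.2 and 1.20 × 4 = 4.8 containers a day, which is what the table's three rows are built to show.

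**The case against.** The strongest reply is that this is a self-evident slip with little reach. The intent can be recovered from the definition of days that follows the formula. The derivation will be set out in ADaM specifications that are not visible here, and programming is subject to validation. A table with every patient at about a third or less would be noticed at a dry run. The listing also shows used and expected counts next to the percentage, so a reader could see that 224 of 224 is not 25%. Overdose has its own reporting route in Protocol Section 12.9 and its own adverse-event outputs in the SAP. Finally, 8 containers a day could not be sustained on the supply assumed above.

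Much of this is fair on scale. The above-120% row is not the only record of over-use, and 8 a day serves only to show how insensitive the formula is: the full-use score of 25% makes the point without it. None of it corrects the text. The footnote would still print the wrong formula under the table. SAP Section 8.1 requires departures from the planned analysis to be justified and recorded in the study report, so a silent repair in programming is not the clean route.

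One further objection stands in part. Dividing by 4 times days is not exactly the same as dividing by an expected container count if that count allows for partial days. Protocol Section 9.2 allows fewer drops on Day 1. As an assumed example, 2 doses on Day 1 and 1 on Day 56 give 2 + 54 × 4 + 1 = 219 containers. That is 100% of such a count but 219 / 224 = 97.8% of 4 × 56. The gap is about 2 points, and either version is sound for this purpose.

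**Conclusion.** The formula is wrong as written in all three places. It returns one quarter of true compliance for any treatment duration, so full use scores 25% and every patient with plausible use falls below 80%. The 25% and 50% scores rest only on 4 containers per day and the written formula. The 35.7% and 71.4% scores also depend on the assumed supply of one 40-container kit per 7 days.

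The damage is confined to the categories in Table 14.1.5.1 and the non-compliance label in Listing 16.2.5.1.2. The continuous summary is scaled down by 4 in every arm, so arms can still be compared on it. The mITT primary analysis is unaffected. The per-protocol set would be affected only if the blinded data review used this figure; Section 6.4 leaves the exclusion criteria to that meeting, and nothing in the documents says that it will. The correction should be made, but no efficacy conclusion depends on it.

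**What to change.** In SAP Section 9.7 and in the footnotes of Table 14.1.5.1 and Listing 16.2.5.1.2, define:

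compliance (%) = number of used BFS containers / (4 × actual number of days of treatment) × 100.

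Deleting the leading 4 and keeping the expected container count would also serve. Use one version in all three places, and apply it to the visit-to-visit intervals with the days of each interval.

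The cost is wording in one SAP section and two shell footnotes. Container counts and dates are already collected, and no analysis set or efficacy result changes.

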9.2 Dosage Schedule

Patients will be directed to administer, by themselves or with assistance from a relative or caregiver, 1 drop of study drug (approximately $25~\mu L$) 4 times a day at 4-hour intervals ($\pm~30~\text{minutes}$) starting in the morning in the study eye, for the duration of the 8-week double-masked treatment period. If a drop does not reach the eye during study drug administration, a second drop should be administered from the same BFS container.

The total daily dose for the vehicle and 5, 25, and 50 μ g/mL arms will therefore be 0, 0.5, 2.5 and 5 μ g/day.

On Day 1, the total number of drops administered may be adapted depending on the time of first dose administration (ie, a decreased number of administrations may occur if treatment is started in the afternoon).

On Day 7/Visit 3 (± 1 day), the first 24 patients enrolled in the study will be required to take their first daily dose of study drug at the study site.

Administration of any other topical treatments in the eye is required to take place at least 15 minutes before or after REC 0/0559 administration, and it is highly recommended to administer other topical treatments at least 1 hour before or after REC 0/0559 administration.

If clinically required, study drug can be continued, temporarily interrupted, or stopped at the discretion of the investigator, as described in Section 8.4.1. If study drug is interrupted, when medically possible and indicated, study drug should be restarted.

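### SAP 9.7 keeps investigator-ordered pauses in the compliance denominator, so compliance is understated for patients who restart after one

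*SAP*

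**What the plan says.** SAP 9.7 divides containers used by containers expected. The denominator and multiplier are printed as "4 * (number of BFS to be used based on actual number of days of treatment)] * 100", and the day count is defined by "Actual number of days = (last treatment administration date) - (first treatment administration date) + 1". The limits follow: "Noncompliance is defined as taking less than 80% or more than 120% of study drug during any outpatient evaluation period". The footnotes to Table 14.1.5.1 and Listing 16.2.5.1.2 repeat the formula, and neither makes any allowance for interruptions.

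SAP 9.6 starts from the same first-to-last span for exposure but treats interruptions differently. It covers those decided by either party ("In case the treatment dosing is interrupted by either the patient or investigator, the number of subjects with interruptions will be summarised") and then states: "This interruption duration is also subtracted from the extent of exposure duration". The footnote to Table 14.3.4.5.1 confirms the subtraction.

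Protocol 9.2 foresees such pauses: "If clinically required, study drug can be continued, temporarily interrupted, or stopped at the discretion of the investigator". It also expects dosing to resume: "If study drug is interrupted, when medically possible and indicated, study drug should be restarted".

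**The concern.** A pause followed by a restart lies between the first and last dose dates, so SAP 9.7 counts it in full. No container is due on a day when the investigator has stopped dosing, yet four are expected. The patient is scored as having under-used the drug while doing what was asked. The section labels its quantity as actual treatment days but computes elapsed days, and the section just before it removes the same days. Neither document reconciles the two.

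At stake is whether Table 14.1.5.1 and Listing 16.2.5.1.2 describe patient behaviour or mix it with investigator decisions.

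**Working it through.** The documents give no compliance result, so there is no stated figure to reproduce. The check is direct arithmetic.

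**Inputs**
- Day count: last − first + 1 (SAP 9.7).
- Containers per day: 4 (Protocol 9.1). The kit agrees: 4 pouches × 10 = 40 containers, for 7 days plus 3 spare, and 10 × 4 = 40.
- Span: 56 days (8 weeks). The ±3-day window of the Day 56 visit gives roughly 53 to 59.
- Limits: below 80% or above 120% (SAP 9.7).
- Assumption: k whole days of investigator-ordered pause inside the span, and 4 containers used on every other day.

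**Step 1: the formula as printed.** Containers to be used over 56 days are 4 × 56 = 224. The bracket multiplies by 4 again, giving 896, so a perfect patient with no pause scores 224 / 896 = 25%. This is a separate fault. From here the denominator is read as 4 × days.

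**Step 2: effect of a pause.** Compliance = 4(56 − k) / (4 × 56) = (56 − k) / 56.

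| Pause k (days) | Reported | Correct |
|---|---|---|
| 0 | 100.0% | 100% |
| 3 | 94.6% | 100% |
| 7 | 87.5% | 100% |
| 11 | 80.4% | 100% |
| 12 | 78.6% | 100% |
| 14 | 75.0% | 100% |
| 21 | 62.5% | 100% |

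**Step 3: crossing 80% overall.** (56 − k) / 56 < 0.80 requires k > 11.2, so 12 days. For a 53-day span it is 11 days (42/53 = 79.2%); for 59 days it is 12 (47/59 = 79.7%).

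**Step 4: visit-to-visit figures.** The programming note to Table 14.1.5.1 asks for compliance per visit interval, but the SAP gives no interval denominator. Assuming the same rule with interval days, 2 paused days of 7 give 5/7 = 71.4%, and 3 of 14 give 11/14 = 78.6%. Both are below 80%.

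**Step 5: no restart.** The last dose date closes the span, so days after it never enter. The patient's compliance is unaffected.

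**Step 6: with paused days removed.** 4(56 − k) / [4(56 − k)] = 100% for any k. If the extra 4 is left in, the result is 25%, so both corrections are needed.

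**Step 7: boundary days.** SAP 9.6 counts an interruption as end − start + 1. Suppose 7 days are recorded and 2 containers were used on each of the first and last of them. Used = 4 × 49 + 4 = 200. Subtracting all 7 days gives 200/196 = 102.0%. Subtracting only the 5 full days gives 200/204 = 98.0%.

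**The case against.** The strongest reply is that exposure and compliance are different quantities and need not share a duration. Protocol 9.5 sets the 80% and 120% limits without exempting interruptions, so compliance might be meant against the planned regimen. The information is also disclosed elsewhere: Table 14.3.4.5.1 reports interruptions by investigator and by patient, with their duration, in each arm. Listing 16.2.5.1.1 gives dates, who decided and doses missed.

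Part of this stands. The two durations may differ, and a reader can trace a low figure back to a pause. But measurement against the planned regimen does not fit the SAP's label of actual treatment days. Nor does it fit the formula, which already drops planned days after a permanent stop. Disclosure in another table does not move a patient out of the <80% row.

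A reader might infer that anyone whose drug was paused is reported as non-compliant. The arithmetic does not support that: overall compliance stays at 80% or above for pauses of up to 11 days in 56. A reader might also infer that the active-dose arms would look less compliant. The documents give no interruption rates, overall or by arm, so this is conjecture.

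**Conclusion.** The inconsistency is real and minor. As written, SAP 9.7 understates compliance for any patient with an investigator-ordered pause that is later restarted, by k/56 of the total for k paused days in a 56-day span. Overall, the <80% label is reached only from 12 days; per interval, 2 days of 7 would suffice under the assumption stated in the working. All figures assume that the surplus factor of 4 has been removed and that every due dose was taken.

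The consequence is confined to a descriptive table in the safety population and its listing. A further inference, that such patients would be selectively removed from the per-protocol set, is not supported: SAP 6.4 leaves exclusion criteria to the blinded data review, and compliance is not named. It could happen only if that review adopted a compliance criterion, and it would then touch only the supportive analysis. The primary analysis uses the mITT population, and no effect on it is shown.

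**What to change.** In SAP 9.7 and in the footnotes to Table 14.1.5.1 and Listing 16.2.5.1.2:

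- Define expected containers as 4 × [(last − first + 1) − investigator-decided interruption days], overall and for each visit interval. This replaces the present bracket and removes the surplus factor of 4 in the same edit.
- Keep patient-decided interruptions in the denominator, because those are missed doses. State that this differs on purpose from SAP 9.6, which removes both types.
- Count as interrupted only full days without scheduled dosing, so that containers used on boundary days do not push compliance above 100%.

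The cost is a little more derivation work. Listing 16.2.5.1.1 already calls for the interruption dates and who decided, so no new data and no change to patient care are needed.
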